## 12.3 Clinical Safety Laboratory Test Data

### 12.3.1 Data Presentation

The clinical safety laboratory test values will be presented in conventional and/or Système International (SI) units.

### 12.3.2 Urine analysis

For urine dipsticks, for which the results are categorical values (for example, negative, trace, 1+, 2+), the number and percentage of patients will be summarised for each test by visit.

The microscopy results will be listed for patients with findings by assessment time point.

### 12.3.3 Potential Drug-induced Liver Injury (DILI)

Signals of DILI will be assessed according to the FDA guideline using the following criteria:

- alanine aminotransferase (ALT) or AST >2×-, >3×-, 5×-, 10×-, or 20×ULN
- total bilirubin (BILI) >2×ULN
- alkaline phosphatase (ALP) >1.5×ULN

- ALT or AST  $>3\times$ ULN and BILI  $>1.5\times$  or  $>2\times$ ULN

In addition, assessment time points for patients for whom Hy's Law is potentially fulfilled will also be flagged in the listing (pHYL):

- ALT or AST  $>3\times$ ULN AND
- BILI  $>2\times$ ULN AND
- ALP  $<2\times$ ULN

In the summaries, each patient should be counted only once using the maximum assessment, or the most severe for the combined criteria.

Patients fulfilling any of the individual criteria (ALT/AST, ALP, or BILI) will be listed, and the listing will include all available ALT, AST, BILI, and ALP, BILI, EOSLE, and GGT values (absolute and normalised), sorted by assessment date in ascending order.

Evaluation of potential Drug-Induced Serious Hepatotoxicity (eDISH) will also be done by plots. Scatter plots of maximum ALT/AST versus maximum BILI will be presented. The criteria for the individual tests will be considered separately (that this means that the maximum of ALT/AST and the maximum BILI may not occur at the same assessment timepoint). The values will be normalised by the ULN (unit  $\times$ ULN) and the X-and Y-axes will be on the log scale. The plot will include a reference line for ALT/AST values  $>3\times$ ULN, and a reference line for BILI values  $>2\times$ ULN. Four quadrants are defined by the reference lines, where the right upper quadrant being the most specific indicator for a drug's potential for causing serious liver injury (Hy's law quadrant).

Subject line plots with values-by-time for ALT, AST, ALP, BILI, GGT and EOSLE (overlaid in the same plot) will be generated for patients with ALT/AST  $> 3\times$ ULN. The test values will be normalised by the ULN (unit  $\times$ ULN) and the Y-axis will be on the log scale. All assessments will be included, and the time will be days since first IMP. Reference lines for the day of first-and last IMP will be included. If there is more than one assessment at the same time point for a test, the maximum value will be used.

For further details, see [Data Handling Plan](#).

#### **12.3.4 Changes in Fasting and non-fasting Lipid and Glucose Concentrations**

Shift tables displaying the change in classification for fasting and non-fasting lipids and fasting and non-fasting glucose from OLEXA to any post-baseline visit will be provided for each test and include the numbers and percentages of patients.

#### **12.4 Vital Signs and Weight**

Descriptive statistics for the vital sign parameters will be presented by visit and the last assessment in the Period.

## 12.5 ECGs

Shift tables displaying shifts from normal to abnormal ECG findings from OLEXA to the Withdrawal/Completion Visit will be provided and include the numbers and percentages of patients.

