8.4 Withdrawal Visit

Patients who withdraw from the study prior to the Completion Visit will be asked to attend a Withdrawal Visit, if at all possible. The visit must be scheduled as soon as possible after withdrawal.

No new information will be collected from patients who withdraw, except information collected in relation to the scheduled Withdrawal Visit or needed for the follow-up of adverse events (section 10.5).

The reason for withdrawal must be recorded on the *Reason for Withdrawal Form*.

For a patient and/or his or her legal representative (if applicable) who withdraw assent/consent:

- if the patient and/or his or her legal representative (if applicable) withdraw assent/consent during a visit and then agrees to it being the final visit, the investigator will complete the visit as a Withdrawal Visit and all the data collected up to and including this visit will be used
- if the patient and/or his or her legal representative (if applicable) withdraw assent/consent during a telephone conversation, the investigator will ask the patient if he or she will attend a Withdrawal Visit. If the patient:
 - agrees to attend a Withdrawal Visit, all the data collected up to and including this visit will be used
 - refuses to attend a Withdrawal Visit, the investigator should attempt to follow the patient's safety and future treatment; any information collected will only be recorded in the patient's medical record

- if the patient and/or his or her legal representative (if applicable) explicitly request that his or her data collected from the time of withdrawal of assent/consent onwards not be used, this will be respected

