## 12.2 General Methodology for Other Safety Data

Unless otherwise specified, tables, graphs, and listings will be based on the APTS, and the tables will be presented for all patients and by lead-in study and by lead-in treatment.

The denominators for the summaries of a given variable will be based on the number of patients with non-missing values at a given visit or during the assessment period.

Descriptive statistics for the safety variables, both absolute values and change from baselines (baseline at randomisation in lead-in study and OLEXA), will be presented by visit and for the last assessment. All available post-OLEXA assessments will be included in the identification of the last assessment.

The number and percentage of patients with at least one PCS value at any post-baseline assessment time point will be summarized by variable. All available assessments will be included in the evaluation of PCS values.

The number and percentage of patients with values out-of-reference range and/or PCS range will be summarized by variable, visit, and last post-baseline assessment.

For patients with post-baseline PCS values, listings will be provided including all the values for those patients for the variable, with flagging of PCS values and out-of-reference-range values.

The PCS definition will be provided by H. Lundbeck and are stated in [Appendix IV](#).

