Recent and concomitant medication	✓ g	✓	✓	✓	✓	✓	✓	✓	✓	✓	✓	✓	✓		
Pregnancy test j	✓ e				✓								✓		
Drug and alcohol screen e,k															

a This visit should take place as soon as possible after the patient withdraws from the study.

b This can be a telephone contact, unless an SAE has occurred since the last visit or unless there was a clinically significant abnormal safety laboratory test value at the last visit. In such cases, safety follow-up(s) must be scheduled to allow for a medical examination and/or blood/urine sampling. Further safety follow-up visits beyond 30 days may be needed as judged by the investigator (if further safety follow-up visits are performed, these must be recorded in the patient's medical record, and not in the eCRF).

c A telephone contact. The patient and/or legal representative and/or the investigator can request an unscheduled site visit to discuss their current dose. During such an unscheduled site visit, the CDRS-R, CGI-S, CGI-I, PAERS and C-SSRS must be performed.

d If the date of a patient visit does not conform to the study plan, subsequent visits should be planned to maintain the visit schedule relative to Baseline Extension A. The number of days between 2 visits must not exceed the number of days for which IMP is provided for in the drug kit.

e Values from assessments and procedures conducted at Visit 12 (Completion Visit) of Study 12709A or 12710A will be the Baseline Extension A Visit values for this study (12712A).

f The assessment of the CGI-I should be in reference to Baseline A in the lead-in studies.

g Ongoing adverse events and concomitant medications (at Completion Visit 12 in Study 12709A or 12710A) will be transcribed to the eCRF Adverse Event Form and Concomitant Medication Form.

h Only for adverse events ongoing at Completion/Withdrawal and new SAEs.

i The 12712A Hormones panel is to be collected using a separate study-specific kit

j Females >10 years of age or female patients at lower age judged by the investigator to be of childbearing potential. Additional pregnancy tests during the study will be performed according to local requirements.

Females <11 years will be tested using a urine hCG test and females >11 years will be tested using a blood hCG test.

- k It is not mandatory to screen for drugs and/or alcohol. However, it can be performed at any visit, at the discretion of the investigator.

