**Table 3 Lundbeck PCS Criteria for ECG Parameters**

ECG Parameter	CDISC Term	Unit	PCS LOW	PCS HIGH
Absolute Time Interval				
PR interval	PRMEAN	Msec		≥ 260
QRS interval	QRSDUR	Msec		≥ 150
QT interval	QTMEAN	Msec		≥ 500
Derived Time Interval				
Heart rate	HRMEAN	beats/min	< 50 and decrease ≥ 15	≥ 120 and increase ≥ 15
QTcB interval	QTCB	Msec	< 300	> 500 or increase > 60
QTcF interval	QTCF	Msec	< 300	> 500 or increase > 60
RR interval	RR	Mses	< 500	> 1200

Increase/decrease is relative to the baseline value

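### The ECG normal-to-abnormal shift table stops at the Completion/Withdrawal Visit, so an overall ECG finding at Week 4 that resolves, or has no final ECG after it, is not tabulated

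*SAP*

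**What the plan says.** SAP 12.5 is a single sentence. It plans "Shift tables displaying shifts from normal to abnormal ECG findings from OLEXA to the Withdrawal/Completion Visit", with numbers and percentages of patients. It names no other time point and gives no rule for a patient without that visit.

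The ECG row of SAP Table 1 (Appendix II) has three entries: Visit 1 (Week 0), Visit 5 (Week 4) and Visit 13 (Week 26, or withdrawal). The Visit 1 entry is taken from the lead-in study: "Values from assessments and procedures conducted at Visit 12 (Completion Visit) of Study 12709A or 12710A will be the Baseline Extension A Visit values". On the final visit, Protocol 8.4 says that patients who leave early "will be asked to attend a Withdrawal Visit, if at all possible".

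SAP 12.2 applies to safety data in general. Descriptive statistics for absolute values and changes "will be presented by visit and for the last assessment". For PCS values, "The number and percentage of patients with at least one PCS value at any post-baseline assessment time point will be summarized by variable". The ECG limits are in Table 3 of Appendix IV, "Lundbeck PCS Criteria for ECG Parameters", which lists PR, QRS, QT, heart rate, QTcB, QTcF and RR.

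The lipid and glucose shift tables in SAP 12.3.4 follow a different rule: they run "from OLEXA to any post-baseline visit will be provided for each test".

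Under Protocol 9.4.7 a paediatric cardiologist at the central laboratory interprets the ECGs, the investigator decides on clinical significance, and abnormalities considered clinically significant are recorded as adverse events.

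**The concern.** An ECG abnormality on treatment can be transient. A comparison of baseline with the end of treatment shows what is present at the end. It does not show what arose during treatment. With two scheduled post-baseline ECGs, the stated rule leaves one of the two overall findings out of the only table specified for ECG findings.

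Two groups drop out of the table:

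- patients newly abnormal at Week 4 whose final ECG is normal;
- patients newly abnormal at Week 4 who have no final ECG.

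The second group deserves more attention, because leaving without a Withdrawal Visit may be related to tolerability. SAP 18.5.1 also treats an assessment as valid only if it falls within 7 days after the last dose. SAP 12.6.2 lifts that rule for PAERS, but nothing in 12.5 lifts it for the ECG shift table. If the rule is applied there, a late withdrawal ECG could be excluded too.

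Long-term safety is the primary objective, and under Protocol 17.10.1 it is addressed by an overall clinical evaluation of the safety results. A reader of the shift table could take it as the count of patients whose ECG became abnormal on treatment, and it would understate that count.

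**Working it through.** **1. ECGs used by the table.** From SAP Table 1, scheduled post-baseline ECGs are Visit 5 (Week 4) and Visit 13, which makes 2. The table in SAP 12.5 uses 1, the Visit 13 or withdrawal ECG.

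**2. Where a new Week 4 abnormality would appear.**

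| Type of Week 4 finding | Output that captures it | Captured? |
|---|---|---|
| Interval or heart-rate value | By-visit summary, SAP 12.2 | Yes |
| Interval or rate beyond a PCS limit | PCS count at any post-baseline time point, and listing, SAP 12.2 and Table 3 | Yes |
| Finding considered clinically significant | Adverse event, Protocol 9.4.7; TEAE tables, SAP 12.1.5 | Yes |
| Overall abnormal finding, still present at an attended final ECG | Shift table, SAP 12.5 | Yes |
| Overall abnormal finding (rhythm, morphology, conduction below the PCS limits), not clinically significant, that resolves or has no final ECG | None clearly specified | No |

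**3. The SAP's handling of comparable data.** Lipid and glucose shifts take any post-baseline visit (12.3.4). The liver summaries take each patient's maximum (12.3.3), C-SSRS the most severe score (12.6.1), PAERS the worst severity (12.6.2), and PCS any post-baseline value (12.2). The Tanner shift (12.6.3) also runs to the end only, but Tanner stage is expected to progress, so an end comparison is natural there.

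**4. Size.** The plan states no figure to reproduce, and no ECG abnormality rate. Let *p* be the share of all 850 planned patients newly abnormal at Week 4, and *q* the share of those still abnormal at an attended final ECG. Both are assumptions.

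New at Week 4 = 850 × *p*. Missed by the shift table = 850 × *p* × (1 − *q*).

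| *p* | New at Week 4 | Missed, *q* = 1 | Missed, *q* = 0.5 | Missed, *q* = 0 |
|---|---|---|---|---|
| 2% | 850 × 0.02 = 17 | 0 | 8.5 (about 9) | 17 |
| 5% | 850 × 0.05 = 42.5 (about 43) | 0 | 21.25 (about 21) | 42.5 (about 43) |

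These are patients missing from the shift table. Some of them would still be seen through the PCS or adverse event outputs in step 2.

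**5. Price of a worst-reading table.** Suppose a patient with an unremarkable heart has a chance *f* of a spurious abnormal reading at each ECG, independently. One reading gives *f*; the worse of two gives 1 − (1 − *f*)². With *f* = 2% this is 1 − 0.98² = 3.96%, and with *f* = 5% it is 1 − 0.95² = 9.75%. Under independence the spurious rate nearly doubles. Spurious readings that recur in the same patient would make the increase smaller.

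**The case against.** The strongest case against is that little of importance is lost. A reader might infer from SAP 12.5 that half of the post-baseline ECG data go unused. The documents do not support that. SAP 12.2 brings Week 4 intervals and heart rate into the by-visit summaries, the PCS counts and the listings. Nor do they support the inference that the primary endpoint is left unanalysed. SAP 3.1 and Protocol 16.1 name ECG parameters and PCS parameter values, which are analysed at Week 4; a normal/abnormal reading is not named there. It would also be wrong to say that the PCS limits ignore conduction, since PR and QRS are both in Table 3. Finally, a clinically significant abnormality reaches the adverse event tables whatever the later visits show. All of this stands, and it confines the point to the residue in the last row of the step 2 table.

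It can also be argued that SAP 12.2, read with SAP 5 (counts and percentages for categorical variables), already implies a by-visit count of ECG findings. That is possible but not clear. The sentence in 12.2 concerns absolute values and changes, and where the SAP wants categorical counts by visit it says so, as for urine dipsticks in 12.3.2. A by-visit count would also not show who shifted from normal.

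The last argument is that an end-of-treatment shift answers a legitimate question in a long-term study, while a worst-reading shift sets several readings against a single baseline one with no concurrent control. This is fair. It is a reason to keep the end-visit table and to annotate the added one. It does not justify omitting Week 4.

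**Conclusion.** The point holds with a narrow scope. Under the stated rule the shift table omits a new overall ECG abnormality at Week 4 when it resolves or when there is no final ECG, and no other Week 4 tabulation of that finding is clearly specified. What is at risk is mainly rhythm, morphology and sub-threshold conduction findings that are neither PCS values nor considered clinically significant.

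The effect is modest and cannot be fixed from the documents. The range of 17 to 43 rests on an assumed 2% to 5% rate in 850 patients. It counts all new Week 4 abnormalities and equals the number missed only if none is still present at an attended final ECG. Reading it as the expected loss would go beyond the documents. The change is still worth making, because ECG safety is part of what the study has to describe and the correction is cheap.

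**What to change.** In SAP 12.5, keep the Completion/Withdrawal table and add a second one: shift from OLEXA to the worst post-OLEXA ECG reading, where a patient counts as abnormal if any scheduled or unscheduled reading is abnormal. This follows the rule in SAP 12.3.4. State whether the 7-day validity rule in SAP 18.5.1 applies to either table, and show the number of patients with no final ECG beside the end-visit table.

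The cost is one extra table from data already collected, with no change to visits or procedures. The statistical cost is the one in step 5: taking the worst of several readings against a single baseline reading raises the shift rate somewhat by chance. A footnote should say so, and the two tables should be read together.

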## 12.6 Other Safety Endpoints

### 12.6.1 Columbia-Suicide Severity Rating Scale (C-SSRS) Scores

The C-SSRS was assessed after OLEXA using the *Since Last Visit Version*

The numbers and percentages of patients with suicide-related events based on the C-SSRS will be summarized for each category of suicidal ideation (items 1-5) and suicidal behaviour (items 6-10). The most severe score (**Panel 6**) per patient related to suicidal ideation and/or behaviour will be summarized.

The number and percentage of patients with *no suicidal ideation or behaviour* will be summarized. Patients in this category are those who:

- answered 'no' to all ideation and behaviour questions; that is, answered 'no' to items 1 to 5 (related to suicidal ideation) and answered 'no' to items 6 to 10 (related to suicidal behaviour)

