9.4.10.1 Columbia-Suicide Severity Rating Scale

The C-SSRS³⁵ is a semi-structured interview developed to systematically assess suicidal ideation and behaviour of patients participating in a clinical study. The C-SSRS has 4 questions addressing suicidal behaviour, 5 questions addressing suicidal ideation, and sub-questions assessing the severity.

In this study, the “Since last visit” version will be applied.

An age-appropriate version of the C-SSRS will be used.

An experienced clinician can use the C-SSRS after a short training session. It takes approximately 5 minutes to administer and rate the C-SSRS.

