#### **12.1.10 Adverse Events of Special Interest**

Treatment-emergent nausea (preferred term), vomiting (preferred term), insomnia (defined below), and sexual dysfunction (defined below) will be summarised. TEAE related to the musculoskeletal SOC will be summarized.

Insomnia related adverse events and sexual dysfunction related adverse events are defined in [Panel 4](#) and [Panel 5](#).

---

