#### Panel 6 C-SSRS Scores

C-SSRS Score	Related to:
1 Wish to be dead	Suicidal ideation
2 Non-specific active suicidal thoughts	
3 Active suicidal ideation with any methods (not plan) without intent to act	
4 Active suicidal ideation with some intent to act, without specific plan	
5 Active suicidal ideation with specific plan and intent	
6 Preparatory acts or behaviour	Suicidal behaviour
7 Aborted attempt	
8 Interrupted attempt	
9 Non-fatal suicide attempt	
10 Completed suicide (only applicable for the post-baseline assessments)	

In the C-SSRS, non-suicidal self-injurious behaviour is captured as a different behaviour; patients may have reported non-suicidal self-injurious behaviour in addition to suicidal ideation/behaviour. Positive responses to non-suicidal self-injurious behaviour will be summarised separately.

For patients with any post-baseline suicidal behaviour (C-SSRS scores of 6 to 10), listings will be prepared including all C-SSRS scores; C-SSRS scores related to suicidal behavior will be flagged.

All assessments will be regarded as valid for C-SSRS.

Missing C-SSRS scores will not be imputed.

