## 17 Changes to Analyses Specified in the Protocol

The following changes have been made as compared to the latest version of the protocol:

- C-SSRS categorisation has been updated and will no longer include C-CASA.
- Treatment emergent adverse events (TEAE) in 12712A is defined as an adverse event that starts or increases in intensity or seriousness after visit 1 of study 12712A.
- The analyses regarding time to first relapse and time to first loss of remission have been removed
- The analysis of random slope and intercept has been removed

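### The suicidality summary in SAP 12.6.1 rests on C-SSRS interviews alone, with no suicide/self-injury AE search and no reconciliation with SAE and death data

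*SAP*

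**What the plan says.** SAP 12.6.1 states: "The numbers and percentages of patients with suicide-related events based on the C-SSRS will be summarized for each category of suicidal ideation". The same sentence extends this to behaviour (items 6 to 10). The section also reports each patient's most severe score and a row for patients with neither ideation nor behaviour, which is defined purely by negative answers to all ten items.

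Two data rules follow Panel 6: "All assessments will be regarded as valid for C-SSRS" and "Missing C-SSRS scores will not be imputed". Panel 6 includes a score for death by suicide: "10 Completed suicide (only applicable for the post-baseline assessments". The protocol describes the instrument differently (9.4.10.1): "The C-SSRS has 4 questions addressing suicidal behaviour, 5 questions addressing suicidal ideation, and sub-questions assessing the severity". So the protocol counts four behaviour questions and the SAP tabulates five behaviour scores.

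On adverse events, SAP 12.1.10 says: "Treatment-emergent nausea (preferred term), vomiting (preferred term), insomnia (defined below), and sexual dysfunction (defined below) will be summarised". It adds the musculoskeletal system organ class, and gives term lists for insomnia and sexual dysfunction. Suicidality and self-injury are not on the list.

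On follow-up, Protocol 5.3 makes a suicide attempt a reason for mandatory withdrawal, and Protocol 8.4 says: "Patients who withdraw from the study prior to the Completion Visit will be asked to attend a Withdrawal Visit, if at all possible". In SAP Appendix II, Table 1, the C-SSRS is ticked at Visits 1 to 13 and not at Visit 14, where only AEs still open and new SAEs are recorded.

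SAP 17 records that "C-SSRS categorisation has been updated and will no longer include C-CASA".

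**The concern.** C-SSRS categorisation is a component of the primary safety endpoint (Protocol 16.1, SAP 3.1). Suicide risk also drives an exclusion criterion, a withdrawal rule and an SAE reporting rule. A reader of the study report will look to the 12.6.1 table for how many patients had suicidal ideation or behaviour.

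That table can only count what an interview recorded. The protocol does carry information from the C-SSRS to the safety database, because ideation at level 4 or 5 must be reported as an SAE (10.1.1). Nothing carries information the other way. An event known to the study only through an AE or SAE form cannot change the table, so any error from this cause makes the table too low. The all-negative row has the reverse problem: it can include a patient whom the study's own SAE data show to have attempted suicide.

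**Working it through.** **Step 1. Planned size.** This is the only stated figure near the point. SAP 15 gives 1200 randomised, 15-20% lead-in dropout and at most 85% roll-over. 1200 × 0.85 × 0.85 = 867 and 1200 × 0.80 × 0.85 = 816, so the stated 850 lies within the range. It serves below only as an illustrative denominator.

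**Step 2. Where each kind of event is reported.**

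| Event | C-SSRS summary (SAP 12.6.1) | Other outputs |
|---|---|---|
| Attempt followed by any interview, including a late Withdrawal Visit | Counted: the protocol uses the since-last-visit form and the SAP sets no date limit | AE, SAE and withdrawal outputs by preferred term |
| Attempt, then withdrawal with no further interview | Not counted | AE, SAE and withdrawal outputs by preferred term (SAP 12.1.5, 12.1.7, 12.1.8) |
| New SAE between Visit 13 and Visit 14 | Not counted: no C-SSRS at Visit 14 | SAE outputs; the treatment-emergent definition in SAP 12.1.2.3 has no end date |
| Death by suicide | Score 10 exists, but no rule says how it is filled without an interview | AE overview (12.1.3), death listing (12.1.6), SAE outputs |
| New non-serious event in follow-up | Not counted | None: not collected at Visit 14 |
| Consent withdrawn by telephone and visit refused | Not counted | None: later information stays in the medical record (Protocol 8.4) |

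The middle three rows are the gap that an analysis change can close. The last two cannot be closed from the study database.

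**Step 3. The all-negative row.** Take a patient with ten negative answers at every attended interview who then attempts suicide, is withdrawn and is not interviewed again. Every available answer is no, missing scores are not imputed, and no AE condition applies. The patient meets the definition of the row. A patient with no interview at all after baseline would instead drop out of numerator and denominator, because SAP 12.2 uses patients with non-missing values.

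**Step 4. Size, by assumption.** The documents give no event counts. Let c be the patients with suicidal behaviour found by C-SSRS and a those known only from AE/SAE data. The share missed is a / (c + a), which does not depend on the denominator. With a = 2:

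- c = 5: 5/850 = 0.59% becomes 7/850 = 0.82%; missed 2/7 = 29%
- c = 10: 10/850 = 1.18% becomes 12/850 = 1.41%; missed 2/12 = 17%
- c = 20: 20/850 = 2.35% becomes 22/850 = 2.59%; missed 2/22 = 9%

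With a = 1 the shares are 17%, 9% and 5%; with a = 5 they are 50%, 33% and 20%.

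**Step 5. Interview coverage.** Follow-up is 4 of 30 planned weeks: 4/30 = 13% of the time per patient has no C-SSRS.

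**The case against.** The strongest reply is that little is lost. The C-SSRS is done at every scheduled contact up to Visit 13, including the telephone contacts, and at unscheduled site visits held to discuss dose. The since-last-visit form picks up events between contacts, and a late Withdrawal Visit interview counts. A positive C-SSRS answer is itself a trigger for withdrawal, and in those cases the interview already exists. Serious events that escape it are still listed and tabulated elsewhere, and the protocol addresses the primary objective through an overall clinical evaluation (17.10.1), not through one table. All of this stands, and it narrows the gap. It does not give the reader a pooled count, nor does it keep a known attempter out of the all-negative row.

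A reader might infer several stronger points that the documents do not support.

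- *Deaths are left out of the SAP.* They are not: Panel 6 has score 10, and deaths are counted and listed under 12.1.3 and 12.1.6. Only the route into score 10 is missing.
- *Dropping C-CASA caused the gap.* In Protocol 16.1 C-CASA was a way of categorising C-SSRS data. It had the same source and the same limits, and removing it took away no AE group.
- *The most severe non-fatal events are the likeliest to lack an interview.* This is plausible, but no passage shows it.
- *The 13% is the undercount.* It measures interview coverage, not missed events.

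It is also a fair objection that writing AE-only events into scores 9 and 10 would mix investigator reports with interview ratings and conflict with the no-imputation rule. The fix below avoids this.

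**Conclusion.** The point holds in a limited form. The suicidality summary, including its all-negative row, comes from C-SSRS answers only. No suicide/self-injury AE search exists, and no reconciliation with SAE and death data is described. Events with no interview afterwards are therefore dispersed by preferred term across other outputs, and a patient known to have attempted suicide can be tabulated as having no suicidal behaviour.

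The direction of any error is certain: the C-SSRS count can only be too low from this cause. Its size is unknown. The 29%, 17% and 9% in the working are assumed scenarios, and if every event is followed by an interview the loss is zero. The conclusion assumes that the Data Handling Plan, which is not among the documents, holds no reconciliation rule; SAP 12.6.1 does not refer to it, although 12.6.2 does. The change is worth making because this is a component of the primary endpoint and the remedy is cheap.

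**What to change.** 1. In SAP 12.1.10, add a prespecified MedDRA search for suicide and self-injury, with the term list fixed before analysis. Say which terms count as suicidal and which as self-injury without stated intent, since SAP 12.6.1 already reports non-suicidal self-injury separately.
2. In SAP 12.6.1, leave the C-SSRS table as it is. Beside it, add one patient-level summary of suicidal ideation or behaviour from either source (C-SSRS, or a qualifying AE/SAE), from first dose to Visit 14, with the APTS as denominator and the source shown: C-SSRS only, AE/SAE only, or both.
3. In the all-negative row, exclude or footnote patients with a qualifying AE or SAE.
4. State how score 10 is populated when no interview is possible, and reconcile the protocol's four behaviour questions with the SAP's five scores.
5. Do not recode AE-only events as C-SSRS scores.

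The cost is SAP wording, one term list, one table, and some judgement in setting the list. No new assessments are needed. The reported rate may be slightly higher.
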